### **12.5.2 Safety endpoints**

For all safety analyses, the FAS will be used. All listings and tables will be presented for all GEP-NET and PPGL participants as a pooled cohort.

Safety summaries (tables, figures) include only data from the on-treatment period with the exception of baseline data which will also be summarized where appropriate (e.g. change from baseline summaries) and long-term safety assessments which will be summarized separately. In addition, a separate summary for death including on treatment and post treatment deaths will

be provided. In particular, summary tables for adverse events (AEs) will summarize only on-treatment events, with a start date during the on-treatment period (treatment-emergent AEs).

The on-treatment period lasts from the date of first administration of study treatment to 56 days after the date of the last actual administration of Lutathera.

## **Adverse events**

All information obtained on adverse events will be displayed by participant.

The number (and percentage) of participants with treatment emergent adverse events (events started after the first dose of study medication or events present prior to start of treatment but increased in severity based on preferred term) will be summarized in the following ways:

- by primary system organ class and preferred term.
- by primary system organ class, preferred term and maximum severity.

Separate summaries will be provided for study medication related adverse events, death, serious adverse events, other significant adverse events leading to discontinuation, and adverse events leading to dose adjustment.

The number (and proportion) of participants with adverse events of special interest as defined in [Section 10.1.5](#) will also be summarized.

A participant with multiple adverse events within a primary system organ class is only counted once towards the total of the primary system organ class.

## **Vital signs**

All vital signs data will be listed by participant, and visit/time and if ranges are available, abnormalities (and relevant orthostatic changes) will be flagged. Summary statistics will be provided by visit/time.

[figure not shown]
## **12-lead ECG**

1. PR, QRS, QT, QTcF, and RR intervals will be obtained from 12-lead ECGs for each participant during the study. ECG data will be read and interpreted locally.
2. Categorical Analysis of QT/QTc interval data based on the number of participants meeting or exceeding predefined limits in terms of absolute QT/QTc intervals or changes from baseline will be presented. In addition, a listing of these participants will be produced.

All ECG data will be listed by treatment group, participant and visit/time, abnormalities will be flagged. Summary statistics will be provided by visit/time.

## **Clinical laboratory evaluations**

All laboratory data including safety biomarkers will be listed by participant, and visit/time and if normal ranges are available abnormalities will be flagged. Summary statistics will be provided by treatment and visit/time. Shift tables using the low/normal/high/ (low and high) classification will be used to compare baseline to the worst on-treatment value.

## 12.7 Interim analyses

For the interim analysis, population pharmacokinetics (PK) and dosimetry models developed based on adult patients will be used to support justification of adolescent population dose by pooling both GEP-NET and PPGL cohort data. Population PK model will be used to derive adolescent PK metrics (i.e. AUC, Caverage), and assess the similarity of exposure in adolescent population as compared to adult PK. Influence of patient baseline characteristics [REDACTED]

[REDACTED] on the PK will also be explored. Adult [REDACTED] and bone marrow will be used to assess the similarity of E-R relationship between dose and dosimetry for adolescent as compared to that for adults. Dosimetry data pooling from GEP-NET and PPGL cohorts, in relation to the adolescent specific creatinine clearance values and other baseline characteristics [REDACTED] will be explored to confirm that a dose of 7.4 GBq over four cycles would give a median dosimetry value for kidney less than 29 Gy and a median dosimetry value for bone marrow less than 2 Gy.

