#### 4.2 Rationale for dose/regimen and duration of treatment

The modelling and simulation analysis to define the dose in the adolescent population was based on the clinical data from two adult clinical trials, [REDACTED] and approximately 50 subjects were available for analysis. As the principal Lutathera risks are related to renal and bone marrow toxicities, the key objective in this analysis was to investigate the factors influencing the absorbed dose to the kidneys and bone marrow in adults and extrapolate this to the adolescent population (12 to <18 years old) accounting for adolescent specific factors determined from the adult dosimetry model.

The amount of Lu radioactivity administered to an adult patient has to achieve an optimal therapeutic effect of PRRT in the tumors with limited side effects to radiosensitive organs, namely the kidneys and bone marrow. The true threshold of the kidney-absorbed dose that predisposes patients to toxicity has not been accurately determined. Based on data from external beam radiation, commonly accepted values vary from 18 to 23 Gy (Marks et al 2010, Wessels et al 2008, Emami et al 1991, Emami 2013). However, there is growing evidence that PRRT with lutetium (Lu) oxodotreotide is less nephrotoxic (Konijnenberg et al 2007, Bodei et al 2008, Sundlöv et al 2017, Bergsma et al 2016b, and Löser et al 2018). As an example, results by Sundlöv et al 2017 support the dose limit proposed for high risk patients (concomitant risk factors) of  $27 \pm 2$  Gy, while suggesting that patients without risk factors may support a higher kidney dosimetry value. In a study of 323 patients described by Bergsma et al 2016b, where a median number of four 7.4 GBq cycles of lutetium (Lu) oxodotreotide have been administered, no subacute grade 3 or 4 nephrotoxicity was observed. The mean kidney absorbed radiation dose in this study was  $20.1 \pm 4.9$  Gy. No correlation was observed between radiation-absorbed dose to the kidneys and worsening creatinine clearance on long-term follow-up. A similar outcome was obtained also in the NETTER-1 Phase III study, in which the kidney absorbed radiation dose was  $19.4 \pm 8.7$  Gy, with no clinically relevant kidney toxicity observed and no evidence of correlation between creatinine clearance level and kidney absorbed dose.

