For bone marrow, the commonly accepted threshold is 2 Gy (based on historical cohorts of patients treated with I (Bergsma et al 2016b), and here too the clinical relevance for PRRT with lutetium (Lu) oxodotreotide has not been established. Bergsma et al 2016a described the hematological toxicity findings in 320 patients treated with 4 cycles of lutetium (Lu) oxodotreotide (7.4 Gy each). The bone marrow dosimetry was evaluated in a subset of patients (obtaining a mean bone marrow absorbed dose of  $2.0 \pm 0.2$  Gy) and no correlation was found between cumulative bone marrow-absorbed dose and therapy-related persistent hematologic disorder. Similarly, in the NETTER-1 study, in which the estimated mean bone marrow absorbed dose was  $1.0 \pm 0.8$  Gy, no correlation was found between these two parameters. Moreover, a wide heterogeneity between authors in the methodology of bone marrow dosimetry (planar imaging, SPECT imaging, blood samples) makes it difficult to compare between studies.

In view of the above, it is considered that the total doses of  $\leq 29$  Gy and  $\leq 2$  Gy of lutetium (Lu) oxodotreotide, constitute appropriate thresholds for the kidney and bone marrow-absorbed dose by subject, respectively.

The modelling and simulation analyses were therefore conducted to estimate the projected dose in the adolescent population ensuring that median dosimetry estimates are  $\leq 29$  Gy for the kidney or  $\leq 2$  Gy for the bone for four treatment cycles. Results indicate that the covariates important in explaining kidney dosimetry across the adult population [REDACTED]

[REDACTED] These findings were also supported by the prior analysis of Svensson et al 2015 who indicated that patients with inferior

renal function were exposed to higher renal dosimetry values, and also developed hematological toxicity.

Reference values taken from the literature for creatinine clearance levels in an adolescent population suggested limits from approximately 70 – 108 ml/min ([Piepsz 2008](#)), which are in line with adult values when adjusted by body surface area ([Pottel 2017](#)) indicating similar renal function in these two groups.

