### 6.5.1.2 Dose modification based on dosimetry

Patients will have bone marrow and kidney dosimetry (as well as that in other organs) determined following the first treatment using planar imaging and blood clearance (for bone marrow) data. In the exceptional circumstances when dosimetry cannot be done in a particular patient after the first dose, it should be done as soon as feasible upon a later dose.

As discussed in [Section 4.2](#), the dosimetry reference limits are 2 Gy and 29 Gy based on bone marrow and kidney dosimetry, respectively.

Dosimetry data will be analysed by a central lab in an expedited manner, and the result of cumulative radiation dose will be provided to the Investigator for each patient to confirm that

the cumulative absorbed dose for subsequent treatments does not exceed the reference limits indicated above for kidney and bone marrow absorbed radiation doses.

For each patient, the Investigator will receive the results of dosimetry analysis (cumulative radiation dose) before the administration of next Lutathera dose (i.e. before the 2nd Lutathera administration if the dosimetry is done after the 1st dose). In parallel, the Investigator will assess safety data for potential DMTs as described in the [Section 6.5.1.1](#) based on local laboratory test results.

In case that the resulting cumulative radiation dose is within the reference limits specified above, and no DMT criteria are met, the Investigator can administer full Lutathera dose for the next administration. DSMB does not need to be consulted in such case.

In case that the resulting cumulative radiation dose (calculated based on dosimetry analysis) exceeds the reference limits specified above, the DSMB will evaluate the totality of dosimetry, PK and safety data (See [Section 8.3](#) and [Section 8.4](#) ) to assess benefit risk for the patient and advise on whether dosing can continue and at which level. In such cases, the Investigator will be informed of the DSMB recommendation (including documented justification based on all data reviewed) prior to the next Lutathera administration. The ultimate decision on dose modification in such cases will remain with the Investigator.

The detailed guidance on dosimetry assessments will be provided in the dosimetry and imaging manuals. The detailed guidance for assessment of patient data and decision-making process for DSMB will be provided in the DSMB charter.

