## 12.8 Sample size calculation

No formal sample size or power calculations were made in the context of this safety study. The overall sample size of 8 patients (with a minimum of 3 GEP-NET patients) is deemed sufficient to confirm similar organ dosimetry results in the adolescent population compared to the ones in adults.

Modelling and simulation analysis shows that a mean (standard deviation) of the absorbed dose in the kidney of approximately 18 Gy (SD 8) is expected in the adolescent population ([Section 4.2](#)). Assuming a standard deviation of 8, a sample size of 8 patients will produce a two-sided 95% confidence interval with a distance from the mean to the limits that is equal to 6.688.

Additionally, a sample size of 8 patients produces an adequate probability of observing acute toxicities (See [Table 12-1](#)). Indeed, in the phase III NETTER-1 study grade 3/4 adverse drug reactions related to Lutathera treatment were observed in 30% of patients. The probability to detect similar events assuming a true incidence rate of 30% in this study population is 94.2% with 8 patients.

**Table 12-1 Likelihood of observing at least one patient with acute toxicity for a sample size of 8 patients and incidence of acute toxicities**

| Sample size | Acute toxicities true incidence rate, % |      |      |      |      |
|-------------|---|------|------|------|------|
|             | 10%                                     | 20%  | 30%  | 40%  | 50%  |
| 8           | 57.0                                    | 83.2 | 94.2 | 98.3 | 99.6 |

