### 3 Sample size calculation

No formal sample size or power calculations were made in the context of this safety study.

For the interim analysis, the sample size is proposed to be a minimum of five patients across the GEP-NET and PPGL indications, including a minimum of 2 GEP-NET patients. Simulations from adult kidney and bone marrow dosimetry models suggested that a clinical trial that has enrolled between 5 and 10 subjects should have the ability to define the median dosimetry values without significant risk of exceeding pre-defined thresholds. Thus, 5 patients across indication should be acceptable.

Dosimetry at the organs of interest is the key measure in this study and is not expected to differ between PPGL and GEP-NET patients (confirmed by the preliminary data). Therefore, the data on PPGL patients will be included in the interim analysis both separately from GEP-NET and combined with GEP-NET to support the overall comparison between pediatric and adult patients. Safety data, to which PPGL patients will also contribute, will be supplemented with literature that provides further justification for the acceptability of this proposal.

For the primary analysis, the overall sample size of 8 participants is deemed sufficient to confirm similar organ dosimetry results in the adolescent population compared to the ones in adults.

Modeling and simulation analysis shows that a mean (standard deviation) of the absorbed dose in the kidney of approximately 18 Gy (SD 8) is expected in the adolescent population. Assuming a standard deviation of 8, a sample size of 8 patients will produce a two-sided 95% confidence interval with a distance from the mean to the limits that is equal to 6.68.

Additionally, a sample size of 8 patients produces an adequate probability of observing acute toxicities (See Table 3-1). Indeed, in the phase III NETTER-1 study grade 3/4 adverse drug reactions related to Lutathera treatment were observed in 30% of patients. The probability to detect similar events assuming a true incidence rate of 30% in this study population is 94.2% with 8 patients.

Final

**Table 3-1 - Likelihood of observing at least one patient with acute toxicity for a sample size of 8 patients and incidence of acute toxicities**

Sample size	Acute toxicities true incidence rate				
	10%	20%	30%	40%	50%
	8	57.0	83.2	94.2	98.3
					99.6

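### The interim dose check asks whether the median organ dose is below 29 Gy and 2 Gy, although these are per-subject limits, and no planned summary counts patients above them

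*Protocol*

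**What the plan says.** **Where the limits come from.** After reviewing the adult literature, Protocol 4.2 concludes that totals of at most 29 Gy and 2 Gy "constitute appropriate thresholds for the kidney and bone marrow-absorbed dose by subject, respectively". Protocol 6.5.1.2 applies them patient by patient: "the dosimetry reference limits are 2 Gy and 29 Gy based on bone marrow and kidney dosimetry, respectively". Each patient's projected cumulative dose goes to the investigator before the next administration, and a result above a limit goes to the DSMB.

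**Where the median enters.** The same Section 4.2 says the simulations behind the dose were run "to estimate the projected dose in the adolescent population ensuring that median dosimetry estimates are" at or below 29 Gy (kidney) or 2 Gy (marrow). Protocol 12.7 carries this into the interim analysis: pooled dosimetry from at least five patients is explored to confirm that the four-cycle regimen "would give a median dosimetry value for kidney less than 29 Gy and a median dosimetry value for bone marrow less than 2 Gy". SAP 3 supports the interim sample size in the same terms, saying that 5 to 10 subjects give the "ability to define the median dosimetry values without significant risk of exceeding pre-defined thresholds".

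**What else is planned.** The primary dosimetry analysis (Protocol 12.4.1, SAP 2.5.2) is descriptive and has no pass criterion. SAP 2.1 gives the summary statistics for quantitative data as mean, SD, median, minimum and maximum. Protocol 12.5.1 compares individual adolescent values with intervals derived from adults; those intervals are not the 29 Gy and 2 Gy limits.

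**The concern.** The limits describe what one subject may accumulate. The check describes the middle of the group. A median under the limit is compatible with nearly half the patients lying above it, so it cannot by itself support a statement that the flat dose keeps adolescents within per-subject limits.

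This matters because the study's stated aim is to confirm the extrapolated dose, and Protocol 12.7 is the only place in the public text where a numeric dosimetry criterion is attached to that confirmation. A maximum shows whether anyone exceeded a limit, but not how many did. By contrast, the SAP does count patients beyond set limits for liver tests (2.6.4), ECG intervals (2.6.5.1) and vital signs (2.6.5.2). The primary dosimetry endpoint, which has explicit numeric limits, has no such count.

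**Working it through.** **The plan's own figure.** Protocol 12.8 states that "approximately 18 Gy (SD 8) is expected in the adolescent population" and gives a 95% half-width of 6.688 for n = 8. Check: t(0.975, 7 df) × 8/√8 = 2.3646 × 2.8284 = 6.688. It reproduces (SAP 3 prints 6.68). The planning values below are therefore the plan's own.

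**Inputs.**
- Kidney planning values: mean 18 Gy, SD 8 Gy (Protocol 12.8).
- Limits: 29 Gy and 2 Gy (Protocol 4.2, 6.5.1.2).
- Interim n: at least 5 (Protocol 12).
- Marrow: the adolescent prediction is redacted, so the adult NETTER-1 value is used as an assumption. Protocol 4.2 describes NETTER-1 as the study "in which the estimated mean bone marrow absorbed dose was" 1.0 ± 0.8 Gy.
- Assumptions not in the documents: normal doses (lognormal as a sensitivity check), and the raw sample median as a simplified stand-in for the model-supported evaluation in Protocol 12.7.

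**1. Counting.** With n = 5 the median is the third value. It is below a limit whenever at least 3 of 5 are below, so 2 of 5 (40%) may exceed. The patients above the kidney limit need not be those above the marrow limit, so up to 4 of 5 could exceed one or the other while both medians pass.

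**2. Share above 29 Gy** = 1 − Φ((29 − mean)/8).

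| True mean kidney dose | Share above 29 Gy |
|---|---|
| 18 Gy (planning value) | 1 − Φ(1.375) = 8.5% |
| 22 Gy | 1 − Φ(0.875) = 19% |
| 25 Gy | 1 − Φ(0.5) = 31% |
| 27 Gy | 1 − Φ(0.25) = 40% |

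**3. Chance that the median of 5 is below 29 Gy** = P(at least 3 of 5 below), binomial with q = 1 − share above.
- True mean 25 Gy, q = 0.6915: 10q³p² + 5q⁴p + q⁵ = 0.3147 + 0.3527 + 0.1581 = 0.825.
- True mean 27 Gy (40% above): 0.68.
- Exactly one third above: 0.79 at n = 5 and 0.88 at n = 11. More patients do not cure this: while fewer than half exceed, a larger sample makes a median below the limit more likely.

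**4. At the planning values.** Share above 29 Gy is 8.46%. Chance of at least one such patient among 8 = 1 − (1 − 0.0846)⁸ = 0.507.

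**5. Marrow, adult values.** 1 − Φ((2 − 1.0)/0.8) = 1 − Φ(1.25) = 10.6% above 2 Gy. The normal form also puts 10.6% of doses below zero, so it is rough; a lognormal with the same mean and SD gives 9.1%.

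**6. Lognormal sensitivity, kidney.** With mean 18 and SD 8, log-SD = √ln(1 + (8/18)²) = 0.425, and 9.1% exceed 29 Gy. For a third to exceed, the true median must be 29·exp(−0.425 × 0.431) = 24.2 Gy, against 29 − 8 × 0.431 = 25.6 Gy under normality.

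**7. What an exact interval can show.** With no patient above the limit, the Clopper–Pearson 95% upper bound is 1 − 0.025^(1/n): 36.9% for 0/8 and 28.5% for 0/11.

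**The case against.** The strongest reply is that no decision rule is being broken. Protocol 12.7 covers the interim analysis only, is exploratory, and works through population models with creatinine clearance rather than a raw median. SAP 3 uses the median only to justify the interim sample size. No hypothesis is tested anywhere, and the primary analysis has no pass mark. All of this stands, so a pass rate at n = 8 would attach a rule to the primary analysis that the documents do not state.

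Other planned work would also tend to show a large shift. Individual values are compared with adult intervals, and SAP 2.7 overlays adolescent data on adult-model predictions with predictive checks stratified by population. A true mean of 25 Gy lies 7 Gy above the planning value, just beyond the planned half-width of 6.688. This stands too, but none of these comparisons is made against 29 Gy or 2 Gy.

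Exceeding a limit is also not treated as failure of the dose. Protocol 4.2 says the kidney threshold is not accurately known and the relevance of the marrow threshold is not established. NETTER-1, "in which the kidney absorbed radiation dose was" 19.4 ± 8.7 Gy, would by the same normal calculation have 13.5% of adults above 29 Gy (1 − Φ(9.6/8.7)), yet Protocol 4.2 reports no clinically relevant kidney toxicity. That is a reason not to prescribe an acceptable share. It is not a reason to leave the share unreported.

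Finally, values are listed by patient, so with about ten patients a reader could count. And parts of Protocol 4.2, 12.7 and SAP 2.7 are redacted, with modelling detail in a separate plan, so the tail may be handled there. A listing still gives no interval and is not tied to the conclusion drawn about the dose.

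**Conclusion.** The mismatch is real and narrow. The one numeric dose-confirmation criterion in the public text is a group median, set against limits that the protocol defines per subject, and no planned summary counts patients above those limits. At n = 5 the criterion tolerates 2 of 5 above a limit. At a true mean of 25 Gy it would be met about 82.5% of the time with 31% above, given normal doses, SD 8 and a raw median.

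Three stronger readings are tempting, and the documents support none of them.
- A reader might infer that a third or more of adolescents are expected to exceed a limit. At 18 Gy (SD 8) it is 8.5% for kidney; a third would need a true kidney median of about 24 to 26 Gy.
- A reader might infer that the dose is formally passed or failed on the median. The check is interim and exploratory, and the overall assessment also uses safety and tolerability.
- A reader might infer that patients above a limit go unnoticed. Protocol 6.5.1.2 sends each such result to the DSMB.

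What remains is that neither DSMB review nor a listing changes what a median can support as a statement about the dose for adolescents generally. This is a cheap improvement, not a flaw that undermines the trial.

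**What to change.** In Protocol 12.7 and SAP 2.5.2, for the interim and the primary analysis:

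1. Report the number and proportion of patients whose projected four-cycle dose exceeds 29 Gy for kidney, 2 Gy for marrow, or either, with exact (Clopper–Pearson) 95% confidence intervals. The projected dose is already calculated for each patient.
2. Have any statement that the dose is confirmed cite these figures beside the median.
3. Reconcile the per-subject definition in Protocol 4.2 with the median wording in 4.2 and 12.7, saying which quantity each use of the limits refers to.

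If the interim analysis has already been run, the change can still be made for the primary analysis. No limit, dose or dosing rule changes, and no acceptable share is set, because the documents give none.

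The cost is one table and a sentence or two of text. The result may read less favourably, because the intervals are wide: no patient above a limit still leaves an upper bound of 37% with 8 patients, or 28.5% with the 11 enrolled at Amendment 03 if all are evaluable. That width is a fair account of what a study of this size can show about per-subject limits.
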